#### **Program Facilitators:**

At the end of the training period we will conduct a semi-structured interview with the facilitators to gather opinions and overall satisfaction with the training deliver, barriers perceived and suggestions for amendments to the training. These interviews will be conducted by trained project staff in a location agreed by facilitators. Due to COVID-19, the interviews will be conducted over phone or via Zoom.

Qualitative interviews with facilitators will be audio recorded and transcribed by project staff or a HIPAA-compliant transcription service. Transcriptions of the audio files will be coded and analyzed by researchers using thematic analysis and grounded theory, using NVIVO software. Audio files will be destroyed once the information is transcribed. A codebook with a priori codes and emergent themes will be developed after reading a subsample of transcripts. Codes will be subsequently revised and refined. Coding discrepancies and errors will be reconciled by consensus. Emerging themes and the coding/analysis process will be described in a final report.

#### 11) Provisions to Monitor the Data to Ensure the Safety of Subjects

As participation in either branch of this study (POL training or community contacts) involves minimal risk to the subjects, this section is not applicable. (N/A)

#### 12) Withdrawal of Subjects

During the consent processes, potential participants will be informed that the alternative to study participation is not to participate. If participants choose to withdraw, all data collection will stop immediately.

#### 13) Risks to Subjects

A small reasonable risk to participants is their loss of confidentiality. All qualitative interviews for both POLs and community contacts will be conducted in a private space, inside of a large office building in Center City, Philadelphia (TPAC). Risks to privacy will be minimized through staff ethics training, layered data security and by restricting access of sensitive information to

staff members who have a specific need for the information. Risks will also be minimized through requesting an NIH Certificate of Confidentiality.

Though the semi-structured interview guide used to interview POLs after their experience with the program will focus on their experience with the training and with the work in the community, it is possible that POLs may discuss their own personal experiences or those of others. With this possibility, comes the risk that some information may cause an emotional reaction. However, participants will be made aware that they can refuse participation at any time or reschedule the interview. Refusing to participate or rescheduling will not be held against participants. They will also be told to not use names or specific identifying information during the interview, as the interview will be audio recorded.

As part of the CRiSOL training, all POLs will be trained in the ethical treatment of study subjects and subject data with special emphasis in maintaining confidentiality. POLs will offer community contacts the opportunity to answer a sets of questions about their experiences and satisfaction with their encounter with the POL and basic demographic characteristics.

For community contacts, there is no potential risk since the information ask would not be sensitive. But we will minimize the potential for psychological discomfort by informing the participants that they are not required to participate in the study, that they should only share information they feel comfortable sharing, they can refuse to answer any questions or withdraw from the study completely, and that there is no penalty for not participating. Participants will also be informed that their personal information will be de-identified. The POLs who have had the contact with the community contact will not have access to the survey results and will not be involved in data analysis.

The risk of loss of confidentiality for community contacts is very low given the procedures we are using, such as collecting and storing respondent contact information in a different location from survey data and using unique identifiers. All data will be stored in password-encrypted files, and access will only be given to trained, authorized personnel.

#### 14) Potential Benefits to Subjects

### **POLs**

POLs will have the opportunity to learn about the health issues that impact their community and gain multiple skills. The CRiSOL training program expands opportunities to learn valuable information from CRiSOL trainers and services providers in Philadelphia. This training also provides the opportunity to gain leadership skills, including training in motivational interviewing, communication skills and making and scheduling appointments. Additionally, training provides POLs the opportunity to play an active role in addressing the SAVAME syndemic and COVID-19 among Latino immigrants in Philadelphia, which may lead to personal satisfaction and a better sense of connection to their community. This study hopes to provide information to help characterize and address the SAVAME syndemic among Latino immigrants. Since POLs will be drawn from the Latino community in Philadelphia, this knowledge may benefit POLs as well.

The CRiSOL team will be applying to the National Association of Social Workers to qualify the training for an official certificate. This certificate would be able to be used as continuing education credits for POLs if they are Licensed Master Social Workers (LMSWs). This nationally recognized training certificate could be used on POL resumes to improve their job prospects.

To incentivize their participation, POLs will also be offered a \$50 gift card for every two-week period that they remain active in the program after graduating from the POL training program. Remaining active means attending meetings every two weeks, being available for a phone checkin during the week that no group meetings are scheduled. Due to COVID-19, incentives will be dispersed online or through mail, based on feasibility and convenience for the leaders.

For the second year extension, POLs will be offered \$300 gift card for completion of the training phase, and a \$100 gift card every two-week period that they remain active in the program. Additionally, each month participants will receive a \$50 card to cover travel expenses related to their participation in the program. At the of the second year, POLs will receive a \$25 gift card for the completion of the exit interview.

#### Community contacts:

The satisfaction community survey will be offered to all community members who the POLs interact with. Community contacts will also benefit from the informal support and resource referrals that POLs offer.

To incentivize their participation, community contacts will be offered a small token of appreciation for their participation in the satisfaction survey. This token will be an item branded with the CRiSOL and/or Drexel logos, such as a tote bag.

The community contacts that agree to participate in the additional surveys (i.e. base and follow up) will receive a \$25 e-gift card.

#### 15) Vulnerable Populations

Participation in both the POL training program and the community survey will be 18 years or older and identify as Hispanic or Latino. No prisoners or children will participate in this study.

Community contacts who are potentially at risk for or affected by the SAVAME factors, especially violence or HIV/AIDS may be considering vulnerable due to the stigma and sensitive nature associated with this community in the United States. POLs will be trained extensively to understand and address factors leading to vulnerability in specific situations, including situations that arise when working with marginalized groups. When working with particularly vulnerable

groups, it is important to take all ethical considerations into account, to further protect these individuals.

Though this research will not inquire about the immigration status of any individual, there is a chance that POLs may divulge their immigration status in qualitative interviews. To protect these individuals, we will request a certificate of confidentiality.

For the community contact survey, no information about immigration status or contact information will be requested.

The researchers have determined that the project contributes to further knowledge expansion and literature for the target population and all required precautions will be done to confirm ethical execution of the project.

#### 16) Multi-Site Research

This is not a multi-site research study, and as such, this section is not applicable. (N/A)

#### 17) Community-Based Participatory Research

Our community-academic partnership includes members from Drexel University, TPAC, and Temple University. It also includes a licensed clinical psychologist who is a trusted member of the Latino immigrant community in Philadelphia and has a history of collaboration with the PI of this project and with TPAC. TPAC is a non-profit organization that provides the following services:

- direct health and social services
- referrals to racial/ethnic minority and low-income communities
- leadership and certification training
- capacity building
- technical assistance.

TPAC has two locations: one in Center City, catering mostly to South Philadelphia residents; and one in North East Philadelphia, serving residents of North Philadelphia neighborhoods. Our community-academic team is multidisciplinary and has extensive experience in survey methods ([name]); syndemics ([name]); mixed methods and intervention design ([name], [name]); network diffusion measures ([name]), and POL and resilience programming ([name], [name]). The overall project will be guided by the community participatory research (CBPR) principles of co-learning, capacity building, benefits to all partners, and long-term commitment to improve the health and well-being of the community.

#### 18) Sharing of Results with Subjects

Results of this study will be shared with the POLs as well as members of Latino-serving organizations during community meetings (date and time TBD) held at either TPAC, WOAR, or

Nesbitt Hall (Drexel Dornsife School of Public Health building). Efforts will be made to prioritize any interested subjects' setting preferences, including date and time of day. While the meetings will be open to anyone from the community, we do not anticipate to be able to share the results with the survey respondents, as contact information will not be collected.

#### 19) Setting

Recruitment, interviews, and training sessions with POLs will take place at TPAC, located at [name].

Interactions between POLs and community contacts have no pre-determined setting, and will take place in settings that are most convenient for both the community contact and POL, and will be mutually decided by the community contact and POL. Due to COVID-19, these contacts might be held over the phone or online to minimize spread of disease. Efforts will be made to prioritize the community contact's setting preferences, including date and day of time. Recruitment with community contacts will take place at TPAC or a location that the respondent feels most comfortable and allows for privacy. The satisfaction survey will be delivered in this setting. POL's will be given training to ensure that locations chosen protect respondent's confidentiality and maximize respondent's comfort. Examples of locations are private meeting rooms at TPAC, private meeting rooms at Drexel University, etc.

#### 20) Resources Available

We recruited 9 POLs and plan to recruit 720 community contacts. These numbers are based on several factors: a) Resources (funds and personnel) and time available to the project; 2) Previous experience conducting research with Latino populations by the study team; 3) Size of the Latino population in Philadelphia; and 4) Discussions with our community partners.

We expect that at least 8 POLs will continue during the second year. Additionally we plan to recruit 720 community contacts, from which 300 will filled the additional surveys.

Our team has the following **people-based resources** available to us to conduct the study:

• [name] (myself): I am an associate professor in the Department of Community Health and Prevention at the Drexel University Dornsife School of Public Health. My academic training, cultural background, and research experience have prepared me well to direct this study. I have a PhD in health psychology and my postdoctoral work focused on HIV prevention and tobacco control research with Latino populations. I am a fully bilingual Latina. During the last 11 years, I have been serving as PI for NIH-funded research aimed at estimating the risk for HIV infection, identifying risk determinants, and examining health care access among Mexican migrants and immigrants. In recognition of the novelty and potential of this work, I received a Presidential Early Career Award for Scientists and Engineers in 2009. I have served as principal investigator and co-investigator for a number of research studies examining

dedicated building with easy access to a broad range of Drexel university resources, Philadelphia's Center City, and the 30th Street Station transportation hub. This location eases cross-disciplinary collaboration among University programs, allows Drexel students from other academic programs to more easily engage with the school's programming, and further enables the School to closely collaborate with communities in the surrounding neighborhoods. Nesbitt Hall was completely renovated and redesigned to meet the specific needs of a school of public health. The remodeled building includes: innovative research space, cutting edge classrooms, conference rooms with state-of-the-art communication capabilities, numerous open and flexible collaboration spaces, a student lounges, and other amenities. There are two large lecture halls on the first floor, available for School of Public Health use and the entire Drexel community. Several areas are designed to foster collaborative student work. Conference rooms in the School's space are used for administrative purposes, research meetings, committee meetings, doctoral defenses, and instructional classroom purposes. For the purposes of this study, meetings can be scheduled in Nesbitt Hall, and space will be used to store incentives.

POLs and participants will also use space at TPAC, public libraries, and other spaces deemed fit by both POLs and participants for meeting purposes.

Drexel University has medical and/or psychological resources available if necessary through the Drexel University School of Medicine and the Office of Counseling and Health Services. [name] (TPAC) and [name] have also identified themselves as available as psychological resources and have strong connections to any medical or psychological resources that participants might need to utilize.

All individuals that will be assisting with the study will be informed of study processes and resources through meetings. POLs will be made aware of resources through the CRiSOL training.

# 21) Prior Approvals

Research team will request a Certificates of Confidentiality (CoC) to protect research data from forced disclosure in any civil, criminal, administrative, legislative, or other proceeding, whether at the federal, state, or local level. Due to the sensitivity of data collected the CoC will assure the confidentiality of subjects' private information.

#### 22) Recruitment Methods

POLs will be recruited by our community partners from the community. Participants will receive informed consent information prior to the baseline survey. Participants of the POL training may withdraw from the study at any time with no adverse consequences.

PROTOCOL TITLE: Cultivating Resilient and Strong Opinion Leaders (CRiSOL) Program

Protocol Version Date: 03.25.2020

#### 23) Number of Subjects

This study aims to recruit and train 10 POLs and 720 community contacts. And for the second year, aims to retain 8 POLs and recruit a total 720 community contacts.

## 24) Confidentiality

Risks to privacy will be minimized through staff ethics training, layered data security and by restricting access of sensitive information to staff members who have a specific need for the information.

- Training: All study staff are trained in the ethical treatment of study subjects and subject data with special emphasis in maintaining confidentiality.
- Data Security: All data files will be encrypted, and password protected with passwords known only to the principle investigator, co-investigators, and graduate students.

## Community contacts:

The data collected from community contacts will be **anonymous** if participants agree to take the "Satisfaction Survey". Throughout the study, the privacy interest of community contacts will be protected, no contact information would be collected for participants. The database will be accessible by selected team members on an "need-to-know" basis and will remain in a password-protected and encrypted folder.

#### 25) Provisions to Protect the Privacy Interests of Subjects

During the consent process, participants will be given the option to not participate in the study and the option to withdraw at any point without having to be penalized.

The nature of the project is voluntary. Throughout the study, we will minimize any potential for discomfort by informing participants that they are not required to participate in the study, that they should only share information that they feel comfortable sharing, and that they can refuse to answer any questions or withdraw from the study at any point. In addition, all surveys will be administered through Qualtrics which is password protected, and will only be accessible from the primary account of the researcher who accesses it. Any data that is downloaded from Qualtrics will be stored on password protected computers and the Drexel OneDrive cloud.

PROTOCOL TITLE: Cultivating Resilient and Strong Opinion Leaders (CRiSOL) Program

Protocol Version Date: 03.25.2020

## 26) Compensation for Research-Related Injury

Not Applicable

#### 27) Economic Burden to Subjects

There is no economic burden unique to the study for the subjects. While CRiSOL is actively working to minimize the economic burden to participants, there may be some economic burden incurred through travel costs to the location of the trainings. CRiSOL is minimizing this cost to participants by hosting trainings at central locations and may consider looking into hosting some trainings in North and South Philadelphia, closer to participants. Economic costs associated with POL work with community contacts is minimal, since POLs will be interacting with the same people who they interact with in the course of their daily lives. The \$50 incentives provided for every two-week period that POLs remain active will help offset this burden.

#### 28) Consent Process

#### POLs:

The research team is responsible for obtaining informed written consent from the participants of the POL training. Written information describing the research will be provided to the subject explaining that the study is voluntary, the purpose of the study, why they were chosen to participate, and what their participation entails. Participants will be provided with investigator contact information should they have any further questions. If the prospective subject agrees to participate, he or she will be asked to sign the consent form.

#### **Community contacts:**

The verbal consent script will be provided to community contacts by POLs before the CRiSOL satisfaction survey. POLs will explain the study to the potential subject, providing all pertinent information and appropriate additional elements of consent disclosure. The research presents no more than minimal risk of harm to the subjects. Written information describing the research will be provided to the subject explaining that the study is voluntary, the purpose of the study, why they were chosen to participate, and what their participation entails. The consent process will take place the day of the interview. Participants will be provided with investigator contact information and will have ample time to ask questions. Participants will provide verbal consent before proceeding with the study.

Prospective participants may speak Spanish. For Spanish-speaking participants, POLs will go over the consent process with the participant and the consent form will be provided in Spanish. The consent process outlined will apply to Spanish-speaking participants as well.

#### Facilitators:

Research team is responsible for obtaining verbal consent prior to the interview. Written information describing the research will be provided to the subject explaining that the study is

voluntary, the purpose of the study, why they were chosen to participate, and what their participation entails. Participants will be provided with investigator contact information should they have any further questions. If the prospective subject agrees to participate, he or she will provide verbal consent before the interview.

#### 29) Process to Document Consent in Writing

#### POLs:

The informed consent process will be explained by either [name], [name], or [name] in either English or Spanish. Written consent will be documented during the initial interview, prior to the POL training.

#### Community contacts:

This study is requesting a waiver of written documentation consent, as the evaluation presents no more than minimal risk of harm to participants. The written script of the consent form provides all written information describing the study and will be provided to all participants. All study participants will provide verbal consent.

#### Facilitator:

This study is requesting a waiver of written documentation consent, as the interview presents no more than minimal risk of harm to participants. The written script of the consent form provides all written information describing the study and will be provided to all participants. All study participants will provide verbal consent prior to the interview.

CRISOL Contigo: a Multi-level Intervention to Reduce the Disproportionate Toll of COVID-19 Among Latino Communities in Philadelphia. (CRISOL Contigo)

[name],
Professor of Community Health and Prevention, Drexel University

ClinicalTrials.gov Identifier: NCT04646616

Other Study ID Numbers: 3R21MD012352-02S1 (U.S. NIH Grant/Contract)

Date: October 28, 2020

Statistical Analysis Plan: CRISOL Contigo Aim 2. Outreach phase.

Summary:

A community popular opinion leader (POL) based intervention to promote measures to reduce COVID-19 risk, transmission, access to testing and treatment, reduction of the impact of COVID-19, and addressing the Substance Abuse, Violence, HIV/AIDS, and Mental health (SAVAME) syndemic in the community. POLs will interact within their networks counseling regarding COVID-19 and SAVAME factors. The POLs will refer individuals to appropriate community services. POLs will record basic sociodemographic characteristics of all community contacts, the issue addressed, and their response to it. The first 300 community contacts will be invited to complete a baseline and 3-month follow up surveys (via internet or phone). The content of the surveys includes: 1) COVID-19 related questions (knowledge, impact, symptoms, risk factors, access to testing and care, acceptability contact tracing, vaccine) 2) Biological risk factors, 3) Social determinants of health, 4) SAVAME outcomes and access to services.

Design: Quasi-experimental (pre-post), pragmatic, single arm, non-randomized, study.

Evaluation of this intervention will be guided by RE-AIM, a comprehensive evaluation framework to gauge a program's public health impact.

Below we outline the Statistical analysis plan of the individual-community contacts level.

The two co-primary outcomes will be:

- 1) Changes in risk of exposure to COVID-19, defined as the availability and/or usage of five modifiable risk factors: Use of mask, frequent hand washing, compliance with physical distance, avoidance of contact with high risk individuals. Combined (added) to create a score. [Time Frame: Baseline and 3 months]
- 2) Number of participants who lack access to health care [Time Frame: Baseline and 3 months]

Secondary outcomes include:

- 1) Number of participants with SAVAME-related factors [Time Frame: Baseline and 3 months]
- 2) Number of participants who lack access to health care [Time Frame: Baseline and 3 months]

Statistical analysis plan.

Baseline and demographic characteristics will be summarized overall for all patients and for those with complete follow up. Univariate summary statistics will be provided for continuous variables and frequencies for categorical variables. Paired t-tests and test of proportions, will be used to assess changes in these outcomes from baseline to 3 months.

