#### Community contacts:

Post interaction with POLs, community members will complete a brief anonymous "Satisfaction Survey" based on their interaction with the POL, in addition to basic sociodemographic

characteristics. Community members will be provided with the informed consent script and must agree to participate before beginning the survey. The CRiSOL survey would be self-administered when the POLs and community contacts meet face-to-face, or administered by the POLs when interactions are made via phone or other media. The latter situation will be the case when social distancing measures are in place due to the coronavirus. The survey relies on Qualtrics®.

Note that by closing the survey, the answers of the individual cannot be accessed anymore except by the research team and no names or identifying information is included in the survey. A small incentive (i.e. a tote bag with the logo of the project) will be given to participants for their time when interactions are done face to face. This will not be possible when interactions are not face to face, such as during the coronavirus crisis.

For this second year, the study will be similar. Community members will complete an anonymous brief "satisfaction survey" after giving verbal consent (use of short consent version). Additionally, for this second year we are adding a new survey. POLs will invite community members to participate and collect phone numbers of the ones that agree. The research team will contact the community members that expressed interest, provide with a copy of the verbal consent and provide a link for them to take the survey. This survey will not collect any personal data. 300 community contacts will be invited to complete a follow-up survey 3 months after the completion of the first survey. The personal information needed to contact participants (i.e. phone number and first name) will be stored in a password-protected document.

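### The binary outcomes, including co-primary 2, have no stated denominator and a test not said to be paired, so differential loss to follow-up can look like a change

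*SAP*

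**What the plan says.** The SAP describes a single-arm pre-post study with surveys at baseline and 3 months.

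- **Test.** The closing paragraph of the SAP states: "Paired t-tests and test of proportions, will be used to assess changes in these outcomes from baseline to 3 months". It gives no analysis set, missing-data rule or sensitivity analysis, and does not say whether the test of proportions is paired.
- **Outcomes.** Co-primary 1 is a score: "Combined (added) to create a score". Co-primary 2, listed again as secondary 2, is "Number of participants who lack access to health care". Secondary 1 is also a count: "Number of participants with SAVAME-related factors [Time Frame: Baseline and 3 months". Neither count has a denominator.
- **Incomplete follow-up.** The only provision is descriptive: baseline characteristics are "summarized overall for all patients and for those with complete follow up".
- **Who the 300 are.** The SAP summary says "The first 300 community contacts will be invited to complete a baseline and 3-month follow up surveys". Protocol section 8 (Community contacts) says "300 community contacts will be invited to complete a follow-up survey 3 months after the completion of the first survey". Protocol section 20 treats 300 as the number who fill in the additional surveys. So 300 may mean people invited to both surveys, people invited to the second, or people who complete them.
- **Methods named elsewhere.** For the opinion leaders, protocol section 10 names McNemar's test for paired binary outcomes. For community-contact data the same section lists generalized estimating equations among its options. The SAP carries neither forward.

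**The concern.** Baseline and 3-month surveys come from the same people, so the yes/no outcomes are paired data. A test of proportions without further description usually means the two-sample test. It can go wrong here in two ways, depending on who is put into it.

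1. *All baseline responders against all 3-month responders.* The two groups differ in membership. If people lacking access to care are harder to reach again by phone or link, the 3-month percentage falls although nobody's access has changed. With one arm, no control group offsets this.
2. *Completers only, but unpaired.* The groups match, but the test ignores within-person correlation and gives up precision.

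The missing denominator makes the choice invisible: a bare count falls whenever people are lost, and a reader could not tell which comparison was made. At stake is one of the two co-primary results.

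**Working it through.** The documents state no power, effect size, SD, baseline proportion or expected retention for these surveys, so there is no figure of the plan's to reproduce. Assumed throughout: 300 people at baseline, two-sided 0.05, and the loss rates shown.

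**1. Unpaired test, all available responders, nobody changes.** Let 40% lack access: 120 lack it, 180 have it. Loss is 50% and 20% respectively.
- Returning: 120 × 0.5 = 60 and 180 × 0.8 = 144, total 204.
- 3-month proportion: 60/204 = 29.4%, against 120/300 = 40.0%.
- Pooled z = (p1 − p2) / √[p(1 − p)(1/300 + 1/204)], with p = 180/504 = 0.357. This gives z = 2.44, p = 0.015.

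Range over assumed inputs (3-month proportion, p-value; the true change is always zero):

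| Baseline lacking access | Loss 30% v 20% | Loss 40% v 20% | Loss 50% v 20% |
|---|---|---|---|
| 30% | 27.3%, 0.49 | 24.3%, 0.15 | 21.1%, 0.025 |
| 40% | 36.8%, 0.46 | 33.3%, 0.12 | 29.4%, 0.015 |
| 50% | 46.7%, 0.45 | 42.9%, 0.11 | 38.5%, 0.012 |

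Restricted to the same people at both surveys, every cell shows a change of exactly zero, because nobody changes.

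**2. Unpaired test on completers.** Take 210 completers, 15% improving and 5% worsening: 31.5 and 10.5 expected discordant pairs, 40% to 30%.
- McNemar: z = (31.5 − 10.5)/√(31.5 + 10.5) = 21/6.48 = 3.24, p = 0.001.
- Two-sample: z = 0.10/√(0.35 × 0.65 × 2/210) = 0.10/0.0465 = 2.15, p = 0.03.

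**3. What pairing does not cure.** Suppose 15% of the cohort (45 people) switch each way, so there is no net change, with loss of 50% v 20% by baseline status.
- Retained: lacking access at both surveys 75 × 0.5 = 37.5; improved 45 × 0.5 = 22.5; worsened 45 × 0.8 = 36; access at both 135 × 0.8 = 108. Total 204.
- Baseline (37.5 + 22.5)/204 = 29.4%. Three months (37.5 + 36)/204 = 36.0%. This is a false rise of 6.6 points (McNemar z = 13.5/√58.5 = 1.77, p = 0.08).
- With 60 improving and 30 worsening, a true 10-point fall, completers show (30 − 24)/204 = 2.9 points.
- Weighting each completer by 1/0.5 or 1/0.8 restores the first case at 3 months: (37.5/0.5 + 36/0.8)/300 = 120/300 = 40%. It works because loss here depends only on baseline status.

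**4. The score (assumed SD 1.2, correlation 0.5, true change +0.20, about 70% retained).**
- Loss driven by the measured baseline score, completers' baseline 0.26 above the cohort's: completer change = 0.20 + (0.5 − 1) × 0.26 = +0.07. Simulation agrees, and a model using all baseline data gives +0.20, each with standard error 0.08.
- Loss driven by a stable personal trait that shifts both visits equally: completers give +0.20, and the all-baseline model gives about +0.31.

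Which analysis is biased depends on why people are lost.

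**The case against.** Three stronger readings are tempting, and the documents do not support them.

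- *That every primary test uses completers only.* This is certain only for the paired t-test on the score. For the yes/no outcomes the SAP is silent. If completers were used at both visits, the shrinking count would disappear, because both visits would share one denominator. The two problems are alternative readings and do not add up.
- *That a falling count is itself a false finding.* The SAP tests proportions, so some denominator is implied. Under random loss the proportion stays at 40% against 40%. A spurious fall would need 300 kept as the 3-month denominator, which the SAP nowhere says.
- *That the paired t-test is invalid unless loss is unrelated to the outcome, and that a repeated-measures model recovers the truth.* The condition is that loss is unrelated to the change. The stable-trait case in step 4 shows completers right and the model wrong.

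The defence has further fair points. Moderate differential loss (40% v 20%) does not reach significance in the table. The planned baseline summary for all and for completers would reveal selection on measured characteristics, although it corrects nothing. This is a pilot, and about 8 leaders are too few for reliable cluster-robust standard errors. All of this stands. It limits the size of the point and the remedy, but it does not supply the missing denominator or pairing.

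**Conclusion.** The point holds in limited form. The SAP leaves open who is counted and whether the data are paired for the yes/no outcomes, co-primary 2 among them. Under the all-responders reading, differential loss alone can produce an apparent change: from about 3 points at 30% v 20% loss to 9 to 12 points at 50% v 20%, the latter significant. Under an unpaired completer reading, the cost is precision (z 2.15 against 3.24 in the example). The paired t-test for the score is acceptable as the main analysis, but loss related to baseline can bias paired completers on either outcome type, so one sensitivity analysis is warranted. All sizes are illustrative, because the documents give no retention, baseline proportion, SD or correlation.

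**What to change.** 1. Define each binary outcome as a proportion, n/N, of the same people with both linked surveys, and test it with McNemar, as the protocol already does for the leaders. Keep the paired t-test for the score.
2. Report retention, with the all-versus-completer baseline summary already planned. State what 300 counts, reconciling the SAP with protocol sections 8 and 20.
3. Add one sensitivity analysis for both co-primary outcomes that uses all baseline responders: for example, weighting by the inverse probability of follow-up, or a repeated-measures model for the score.
4. Confirm that the two surveys can be linked. Protocol section 13 mentions unique identifiers, while section 8 says the new survey collects no personal data.

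The cost is SAP wording and a little more analysis, with no new visits. The sensitivity analysis rests on missing-at-random, which is a different assumption from that of the completer analysis and not a weaker one. Report it beside the main result, not in place of it.
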